3.1.2.2 Maximum Tolerated Dose 2 (MTD2)

[figure not shown]
Dose escalation for the MTD2 following the initial dosing (MTD1) will proceed after MTD1 is determined and implements a dose step. The cohort for which a dose step will be implemented will start treatment for the first dose at the MTD1 assessed in the dose escalation for the first MTD. After this run-in dose, there may be a dose increase to the next higher dose as per the dosing schedule shown in [Table 3](#) of the protocol. If this treatment schedule is tolerated, the following dose cohorts will continue to receive the run in (initial) dose at MTD1 to assess the MTD2. The target (second) dose will be increased until an MTD2 is reached. Testing of an MTD3 will be guided in the same way by the BLRM and the DLRT review after considering all information.

Subjects who complete the DLT period (see [Section 6.2.1.4](#)) may proceed to a higher dose level for the following treatment cycle once the next dose cohort has been deemed safe by the DLRT, after consultation with the sponsor, if the subject has:

- No DLT reported during or after the completion of the DLT period

See [Section 7.2.2](#) for details on assessments applicable in case of intra-subject dose escalation. Dose limiting toxicities experienced by subjects after completing the DLT period will be considered in the BLRM design to account for any late onset toxicity.

Single Subject Cohorts

In the initial dose escalation cohorts, a single subject will be enrolled until any pharmacologic activity (including but not limited to infusion reaction, CRS, drop in white count) is noted. Evidence of pharmacologic activity will trigger multiple subject enrollment in the same and all subsequent cohorts. The initial dose levels are anticipated to be lower than the dose levels at which any clinical activity related to AMG 427 may be observed.

Multiple Subject Cohorts

Once multiple subject cohorts are triggered as described above, the same and subsequent cohorts will enroll 2 to 4 evaluable subjects based on BLRM output.

Time interval between Enrollment of Subjects in Each Cohort

There will be at least a 7-day (168-hour) interval between the start of treatment of the first and second subject in each cohort (ie, at the same dose and schedule). On day 7 of this interval, the site investigator will evaluate all available safety and laboratory data for the treated subject and confirm the occurrence/non-occurrence of a DLT to the sponsor. The sponsor will only be able to open enrollment for the next subject in the cohort after receipt of this confirmation. If deemed necessary, the 7-day interval may be extended until sufficient data are available to allow an assessment of the feasibility of treatment start of the next subject. In addition, there will be at least a 96-hour interval between the start of treatment of the second subject and all subsequent subjects in each cohort. Hence, no more than 3 subjects will be enrolled in 2 weeks.

Intra-subject dose escalation (ISDE)

A subject may receive a dose higher than what they received in the first cycle if:

- the next dose cohort has been deemed safe by the DLRT
- after consultation with the sponsor
- no DLT is reported during or after completion of the DLT period for that subject

- Subjects receiving low, subtherapeutic doses of AMG 427, such as subjects in the etanercept (Enbrel) substudy, may intra-subject dose escalate to a Dose Level Review Meeting (DLRM) approved dose immediately after cycle 1 if they have not experienced a DLT; the DLT window will remain 28 days (21 days if the subject shows disease progression)

3.1.3 Expansion Cohort

At completion of the dose escalation cohorts, approximately 90 additional subjects (approximately 40 R/R AML subjects in the FIH cohorts and 50 MRD+ AML subjects in the MRD+ cohorts) will be enrolled in dose expansion cohorts to gain further clinical experience, safety, and efficacy data in subjects with AMG 427. The dose to be evaluated will be at or below the MTD estimated in the dose escalation cohorts. Once the preliminary MTD and R2PD are established, the FDA will be provided with brief interim results of the dose escalation phase.

In the expansion phase, all available study data will be reviewed (with recruitment ongoing) by the DLRT once every 6th subject has at least completed their first treatment cycle plus 2 weeks or dropped out of treatment/study, whichever occurs earlier. The MTD will be further evaluated by applying BLRM using all available data, including data from subjects in the expansion phase. Ad hoc meetings may be convened any time in case of important safety events (see also Section 6.2.1.3).

Based on emerging safety data, the planned dose level and dose schedule may be modified during the conduct of the expansion phase. Additionally, enrollment to dose expansion will be paused and possibly terminated if safety stopping rules and/or efficacy futility rules are met (see Section 10.3 for details).

A final estimate of the MTD and RP2D using BLRM will be evaluated and confirmed utilizing all DLT-evaluable subjects from the dose escalation and the dose expansion cohorts. For definition of DLT-evaluable, see Section 6.2.1.3. Additional expansion cohorts testing alternative dose levels or biologic subsets may be considered by amendment.

The overall study design is described by a [Study Design and Treatment Schema](#) at the end of the protocol synopsis section.

The study endpoints are defined in Section 10.1.1.

3.2 Number of Sites

This study will be conducted at approximately 15 sites in the US, Australia, Canada, Japan, South Korea, and Germany. Additional countries or sites may be added if necessary.

Sites that do not enroll subjects into an open cohort within 6 months of site initiation may be closed or replaced.

3.3 Number of Subjects

Participants in this clinical investigation shall be referred to as “subjects.”

It is anticipated that approximately 200 subjects will be enrolled in this study, with approximately 110 subjects enrolled in the dose escalation cohorts and 90 subjects in the dose expansion cohorts:

Dose escalation cohorts:

- FIH (R/R AML): approximately 90 subjects
 - **(CLOSED)** etanercept substudy (R/R AML): approximately 25 subjects
- eIV (R/R AML): approximately 10 subjects
- MRD Group (MRD+): approximately 10 subjects

Dose expansion cohorts:

- FIH (R/R AML): approximately 40 subjects
- MRD Group (MRD+): approximately 50 subjects

For ethical and operational reasons subjects who already are in the screening phase at the time of enrollment stop (end of expansion phase) will still be allowed to be treated. Therefore, an over running of subject recruitment might be possible.

Based on emerging data, additional subjects may be enrolled.

The rationale for the number of subjects is provided in Section [10.2](#).

3.4 Replacement of Subjects

Ineligible subjects (eg, subjects who were exposed to investigational product but post hoc were found to be ineligible) may be replaced. During dose escalation, subjects that are not DLT-evaluable will be replaced. See Section [6.2.1.3](#) for definition of DLT-evaluable subjects.

3.5 Estimated Study Duration

3.5.1 Study Duration for Subjects

Dose escalation phase

It is anticipated that an individual subject enrolled in the dose escalation phase will participate in the study for up to 14 months. This includes a screening period lasting up to 14 days, a treatment period lasting approximately 10 to 12 months, and an SFU period lasting approximately 4 weeks after the last dose.

Dose expansion phase

Individual subjects enrolled in the dose expansion phase will participate in the study for up to about 2 years. This includes a screening period lasting up to 14 days, a treatment period lasting approximately 10 to 12 months, an SFU period lasting approximately 4 weeks after the last dose, and an LTFU period lasting up to 2 years after the first dose of AMG 427 (for subjects enrolled in the expansion phase only).

The actual duration for individual subjects will vary depending upon tolerability of AMG 427, evidence of clinical progression, and willingness to participate in the study.

After completion of a first cycle without a DLT, up to 11 additional treatment cycles can be administered as long as, in the judgment of the investigator, the subject is deriving benefit.

3.5.2 End of Study

End of Study (Primary Completion): The primary completion date is defined as the date when the last subject is assessed or receives an intervention for the purposes of final collection of data for the primary endpoint(s), for the purposes of conducting the primary analysis, whether the study concluded as planned in the protocol or was terminated early.

The primary completion date is the date when the last subject either had the opportunity to receive up to 12 cycles of treatment or terminated the study early.

If the study concludes prior to the primary completion date originally planned in the protocol (ie, early termination of the study), then the primary completion will be the date when the last subject is assessed or receives an intervention for evaluation in the study (ie, last subject last visit).

End of Study (For an Individual Subject):

An individual subject is considered to have completed the study if he/she has completed SFU visit for subjects enrolled in the dose escalation phase, or LTFU visit for subjects enrolled in the dose expansion phase as shown in the Schedule of Assessments (Section 7.1). The SFU visit should occur approximately 4 weeks (or up to 7 days thereafter) after the last dose of AMG 427 or prior to the initiation of other AML therapy, whichever occurs earlier.

End of study (EOS) for an individual subject is defined as the last day that protocol-specified procedures/assessments are conducted for the individual subject.

4. SUBJECT ELIGIBILITY

Investigators will be expected to maintain a screening log of all potential study candidates that includes limited information about the potential candidate (eg, date of screening).

Before any study-specific activities/procedure, the appropriate written informed consent must be obtained (see Section 11.1).

4.1 Inclusion Criteria

101. Subject has provided informed consent prior to initiation of any study-specific activities/procedures
102. Subjects ≥ 18 years of age at the time of signing consent
103. For R/R AML subjects only, AML as defined by the WHO Classification ([Appendix D](#)) as persisting or recurring following 1 or more treatment courses (exceptions noted in exclusion criteria). Subjects must have failed treatment with, be intolerant to, or must not be candidates for available therapies for the treatment of R/R AML (not applicable to MRD+ subjects)
104. For R/R AML subjects only, myeloblasts $\geq 5\%$ in bone marrow, as confirmed by immunophenotype by flow cytometry (not applicable to MRD+ subjects)
105. Eastern Cooperative Oncology Group (ECOG, [Appendix F](#)) Performance Status of ≤ 2
106. Renal function as follows:
 - serum creatinine < 2.0 mg/dL (176.84 $\mu\text{mol/L}$)
 - estimated glomerular filtration rate (eGFR) > 30 mL/min/1.73 m²
107. Hepatic function as follows:
 - aspartate aminotransferase (AST) and alanine aminotransferase (ALT) ≤ 3.0 x upper limit of normal (ULN)
 - bilirubin ≤ 1.5 x ULN (unless considered due to Gilbert's syndrome or hemolysis)
108. **(CLOSED)** Etanercept (Enbrel) substudy only:

No active tuberculosis in the setting of anti-TNF therapy

National guidelines should be followed for appropriate tuberculosis screening in the setting of anti-TNF therapy, including a minimum of:

 - Subject has a negative test for tuberculosis during screening defined as either:
 - Negative purified protein derivative (PPD) (< 5 mm induration at 48 to 72 hours after test is placed) OR
 - Negative Quantiferon test

Subjects with positive PPD and a history of bacillus Calmette-Guérin vaccination are allowed with a negative Quantiferon test.

Subjects with a positive PPD test (without a history of bacillus Calmette-Guérin vaccination) or subjects with a positive or indeterminate Quantiferon test are allowed if they have all of the following:

- no symptoms, per tuberculosis worksheet provided by Amgen
- documented history of a completed course of adequate treatment or prophylaxis (per local standard of care) prior to the start of investigational product
- no known exposure to a case of active tuberculosis after most recent prophylaxis
- no evidence of active tuberculosis on chest radiograph within 3 months prior to the first dose of investigational product

109. For the MRD+ Group, AML subjects in any CR/CRh/CRi:

- with detectable measurable/MRD as assessed by local institution

The MRD assessment must have been performed within 3 months of enrollment.

- not eligible for allogenic HSCT per investigator assessment, lacking a donor, or declining the procedure

Subject may have received any induction and consolidation/maintenance regimens, including cytotoxic agents, hypomethylating agents, transplant, or other therapeutics, to achieve CR/CRh/CRi, prior to screening.

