216. Unresolved toxicities from prior antitumor therapy, defined as not having resolved to Common Terminology Criteria for Adverse Events (CTCAE), version 4.0 grade 1 (with the exception of myelosuppression, eg, neutropenia, anemia, thrombocytopenia), or to levels dictated in the eligibility criteria with the exception of alopecia or toxicities from prior antitumor therapy that are considered irreversible (defined as having been present and stable for > 2 months) which may be allowed if they are not otherwise described in the exclusion criteria AND there is agreement to allow by both the investigator and sponsor
217. Antitumor therapy (chemotherapy, antibody therapy, molecular-targeted therapy such as FLT3 inhibitors, or investigational agent) within 14 days of day 1
 - Exception: hydroxyurea to control peripheral blood leukemic cell counts is allowed until start of investigational product treatment
 - Exception: antitumor therapies with short half-lives only require passing of 5 half-lives from last dose, and after discussion with sponsor
218. Treatment with systemic immune modulators including, but not limited to, non-topical systemic corticosteroids, cyclosporine, and tacrolimus within 2 weeks before enrollment (day 1)

- Exception: physiologic replacement steroids or steroids for treatment of transfusion/hypersensitivity reactions
219. Prior treatment with a FLT3 targeting CAR-T
220. Major surgery within 28 days of study day 1 with the exception of biopsy and insertion of central venous catheter
221. History or evidence of any other clinically significant disorder, condition or disease that, in the opinion of the investigator or Amgen medical monitor would pose a risk to subject safety or interfere with the study evaluation, procedures or completion
222. Males and females of reproductive potential who are unwilling to practice a highly effective method(s) of birth control while on study through 4 weeks after receiving the last dose of study drug. Acceptable methods of highly effective birth control include sexual abstinence (males, females); vasectomy; bilateral tubal ligation/occlusion; or a condom with spermicide (men) in combination with hormonal birth control or intrauterine device (IUD) (women)
223. Females who are lactating/breastfeeding or who plan to breastfeed while on study through 4 weeks after receiving the last dose of study drug
224. Females with a positive pregnancy test

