7.2 General Study Procedures

A signed and dated IRB/IEC approved ICF must be obtained prior to performing any study-specific procedures including discontinuing standard therapy for observing a study washout period.

During the study, every effort should be made to perform the study procedures as indicated on the Schedules of Assessments (Table 10 to Table 23). Every effort should be taken to collect all biomarker and PK samples as described in the schedule of assessments. However, if sample processing/shipment on a weekend/holiday is not logistically feasible for a site, this needs to be documented and will not be considered a deviation from the protocol.

Subjects will be seen in the clinic for study evaluations. When electrocardiograms (ECGs), vital signs, blood sample collections, biomarker sample collections, and aspirate/biopsy sample collections occur on the same visit, ECGs and vital signs should be performed before samples (blood, biopsy/aspirate) are collected. Blood samples must not be taken/drawn from the catheter port used for AMG 427 infusion. If a permanent central line with more than 1 lumen is used, blood draws can be done via the lumen that is not used for drug administration (see also Section 7.3.15). The time of blood sample collection must be recorded with the exact time of collection (do not use the time that the samples were frozen or any other time point).

The study specific manuals provide additional details regarding the requirements for these procedures.

Acceptable deviation windows are as follows:

- Infusion duration \pm 10 minute window.
- ECGs, biomarker blood draws (cycles 1 – 3), vital signs (including pulse oximetry):
 - \pm 15 minute window if collected within the first 24 hours (excluding the 24 hour sample) after the start of any dose
 - \pm 2 hour window if collected between 24 hours and 3 days after the start of any dose
 - Assessments after day 3 but within 7 days post infusion start should be performed on the indicated study day, but are not required at a certain hour of the day
 - Assessments after day 7 have a \pm 1 day window
- For R/R AML subjects, bone marrow assessments post treatment start: \pm 3 days

- For MRD+ subjects, bone marrow assessments do not need to be repeated if done within 3 months prior to start of treatment with AMG 427. If more than 3 months have passed, discuss with medical monitor prior to performing.
- PK blood draws in cycles 1 - 3:
 - within 2 hours prior to infusion start

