- Laboratory assessments: hematology, chemistry, coagulation, urinalysis, serum pregnancy test (females only), and hepatitis serology
- Estimated glomerular filtration rate (eGFR)
- Bone marrow assessments
- Serious adverse event reporting
- Documentation of concomitant and rescue medications.

Re-screening:

A subject may be rescreened up to 3 additional times during the study at the discretion of the investigator. The subject must be re-consented if a re-screening attempt occurs outside the 14-day screening period.

Re-screened subjects must be documented as screen failed in the subject's medical record and subsequently documented as re-screened. Subjects will retain the same subject identification number assigned at the time of initial screening. Once the subject

is recorded as re-screened, a new 14-day screening window will begin. The following assessments do not have to be repeated during re-screening if they were performed as standard of care or during the initial screening attempt within the time frames specified below:

- Hepatitis serology does not need to be repeated if it was performed within 6 weeks prior to start of treatment with AMG 427
- Bone marrow assessments (except molecular panel, see last bullet) do not need to be repeated if done within 4 weeks prior to start of treatment with AMG 427 as long as subject did not receive any anti-leukemic therapy in the interim
- Molecular panel on bone marrow does not need to be repeated if done within 3 months of starting AMG 427 therapy

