7.3.15 Pharmacokinetic Blood Sampling

Blood samples will be obtained for determination of serum concentrations of AMG 427 at the time points specified in the Schedules of Assessments ([Table 10](#) to [Table 23](#)). Blood must not be drawn from the port catheter during investigational product infusion and for at least 5 minutes after the end of infusion. End of infusion is defined as end of total infusion time (after investigational product and IV flush infusions). If a permanent central line with more than 1 lumen is used, blood draws can be done via the lumen that is not used for drug administration. However, the preference is for PK samples to be drawn peripherally during infusion. Sample collection, processing, storage, and shipping instructions are provided in a separate laboratory manual.

[figure not shown]

Table 25. Bone Marrow Collections

Test	Time point		
	Screening	D14 (for cohorts receiving D1, ± D3 & 5 doses)/D28 (for cohorts receiving D1, ± D3, 5, 8, 12, 19 doses) for all cycles	Unscheduled
Bone marrow aspirate	Required	Required (unless peripheral blood absolute blast count 20%, in which case bone marrow assessments are optional).	As needed (eg, if infusion-free period is prolonged beyond 4 weeks for cytopenia, bone marrow aspirate must be performed before starting next cycle of AMG 427)
Bone marrow biopsy	Required if aspirate is inadequate (eg, no spicules seen); optional if aspirate is adequate	Optional	Optional
Conventional cytogenetics	Required	Optional	Optional
Immunophenotype (including FLT3/CD135) ^a	Required on BM aspirate	Required on BM aspirate/peripheral blood blasts	Required on BM aspirates/peripheral blood blasts
Molecular panel (NPM1, FLT3 ITD/TKD, IDH1/2, CEBPA etc.)	Required on BM aspirate, within 3 months of day 1 is acceptable	Optional	Optional
Minimal/Measurable residual disease assessment		Required on BM aspirates only for subjects in CR	Required on BM aspirates only for subjects in CR
	Required for MRD+ AML subjects, only if not done within 3 months of enrollment (at local and central laboratory).		

AML = Acute Myeloid Leukemia; BM = bone marrow; C = cycle; CR = complete response;
 MRD = minimal/measurable residual disease; MRD+ = minimal/measurable residual disease-positive;
 R/R = relapsed/refractory; SOA = schedule of assessments

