In this study, MRD assessments will be utilized as both an eligibility/inclusion criteria in the MRD+ cohort, as well as an additional efficacy endpoint for all cohorts. [REDACTED]

[figure not shown]
[REDACTED]. For subjects enrolling in MRD+ group, bone marrow sample for MRD assessment is required for both local and central testing (except at screening visit for subjects with historical test result available < 3 months from start of treatment).

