7.5.2.1 MRD Testing for Screening/Eligibility for MRD+ Group

For subjects to be eligible for study participation in MRD+ groups, bone marrow MRD assessment is required prior to enrollment to establish MRD status; local testing is sufficient for enrollment. Collection of bone marrow aspirate following local standard of care procedure for MRD testing is not expected to present any additional risk to the health, safety, and welfare of the subject. Screening for MRD will be conducted using an investigational diagnostic or validated local test/assay at a CLIA certified laboratory (for US only) agreed upon by the Sponsor; local testing is sufficient for the enrollment decision if the test result is from ≤ 3 months from the start of treatment. If new local testing is performed during screening, additional bone marrow aspirate from the same bone marrow pull is required to be sent for exploratory testing at central lab for these subjects.

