**Event with missing/unknown relationship to treatment will be assumed to be treatment-related.**

#### Dose Limiting Toxicities (DLT)

A DLT will be defined as any of the events described in protocol section 6.2.1.3 occurring in a subject during the DLT window. The DLT window will start on D1 (start of the administration of the first dose) and last for 28 days for all cohorts. Any adverse event occurring outside the DLT window that is determined by the investigator to be possibly related to the investigational product, which is seen more frequently or is more severe than expected or is persistent despite appropriate management, can be determined to be a DLT upon unanimous decision by the DLRT after review of the adverse event and all available safety data. Investigators will determine whether an adverse event qualifies as a DLT per protocol Section 6.2.1.3 and it will be collected by the flag indicating DLT in Events CRF.

Maximum Tolerated Dose (MTD)

The MTD is defined as the highest dose level whose DLT rate has the highest probability of the target TPI, an excessive/unacceptable TPI of < 0.25, and a minimum of 6 subjects have been treated at the MTD.

Overall Response (for R/R AML)

Overall response is defined as any of the following: complete remission (CR), CR with incomplete recovery (CRi), morphologic leukemia-free state, partial remission (all according to Revised International Working Group [IWG] response criteria) or CR with partial hematologic recovery (CRh).

Duration of Response (DOR) (for R/R AML)

Duration of response is defined as the number of days between the date of the first disease assessment indicating an overall response through the subsequent date of progression or relapse as defined by revised IWG response criteria or death due to any cause, or where applicable date of censoring [date of first progressive disease assessment or relapse or death or date of censoring – date of the first objective response result +1]. Subjects who respond and have not progressed or relapse or died while on study will be censored at the last adequate disease assessment date. Subjects who do not achieve an overall response will be excluded from the analysis of duration of response.

MRD Conversion Rate

MRD conversion rate is the number of subject achieve MRD- among subjects at who are MRD+ at enrollment. [REDACTED]

Overall Survival

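### On first screening, the qualifying MRD-positive marrow need not post-date the last anti-leukemic therapy, so negativity from earlier treatment could be counted as AMG 427 conversion

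*Protocol*

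**What the plan says.** **Age of the qualifying sample.** Criterion 109 (Protocol Section 4.1) sets the limit: "The MRD assessment must have been performed within 3 months of enrollment". Section 7.2 waives a fresh marrow: "For MRD+ subjects, bone marrow assessments do not need to be repeated if done within 3 months prior to start of treatment". Section 7.5.2 asks for both local and central marrow testing, "except at screening visit for subjects with historical test result available < 3 months from start of treatment". Section 7.5.2.1 adds that "local testing is sufficient for the enrollment decision if the test result is from ≤ 3 months from the start of treatment". Table 25 likewise asks for a screening MRD test only where no recent result exists. The 3 months are counted from enrollment in criterion 109 and Table 25, and from start of treatment in the other three places.

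**Prior therapy.** Exclusion 217 (Section 4.2) covers antitumor treatment of the listed kinds, "or investigational agent) within 14 days of day 1". Agents with short half-lives need only five half-lives, after discussion with the sponsor. Criterion 109 accepts any earlier induction, consolidation or maintenance regimen and does not place it before the MRD test. The transplant windows in exclusions 206 and 207 bind R/R subjects only; an MRD+ subject inside them may enter after discussion with the sponsor.

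**The one safeguard.** In the re-screening part of Section 7.2.1, a marrow up to 4 weeks old may be reused "as long as subject did not receive any anti-leukemic therapy in the interim".

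**Use of the result.** SAP Section 5 defines the endpoint: "MRD conversion rate is the number of subject achieve MRD- among subjects at who are MRD+ at enrollment". Protocol Section 10.3 and SAP Section 3.3 call a conversion rate below 25% insufficient. They propose stopping at 2 or fewer conversions in 12 subjects, 4 or fewer in 18, or 5 or fewer in 24, in a cohort planned at 50. Protocol Tables 22 and 23 collect whole-blood MRD before the first dose, but no visible text gives it a role in defining baseline.

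**The concern.** Conversion is a change from a baseline state, and here that state may be up to 3 months old. Taking 3 months as 90 days, about 90 − 14 = 76 days can lie between the qualifying sample and the start of the washout. Nothing readable rules out consolidation, hypomethylating or targeted therapy in that interval. A subject who becomes MRD-negative from that therapy would still enter as MRD-positive, and the first on-treatment marrow (day 14 or day 28, Table 25) would show a conversion.

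There is no control arm to absorb the error, and it acts in one direction only: it raises the apparent rate. The same count feeds the futility rule, so a drug with insufficient activity would be more likely to continue to the full cohort.

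**Working it through.** **Inputs from the documents.** Futility looks at 12, 18 and 24 subjects, stopping at ≤2, ≤4 and ≤5 conversions; maximum N = 50; threshold 25% (Protocol Section 10.3, SAP Section 3.3).

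**Assumed inputs.** q is the fraction already MRD-negative on day 1 despite the older positive result. The documents give no value, so a range is shown. Those subjects are assumed to stay negative and be scored as conversions. p is the true AMG 427 conversion rate in the others.

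**Step 1: reproduce the plan's table.** With X_n the conversions among the first n subjects, the probability of stopping by 24 is

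P(X12 ≤ 2) + P(X12 ≥ 3, X18 ≤ 4) + P(X12 ≥ 3, X18 ≥ 5, X24 ≤ 5),

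evaluated exactly from binomial increments. For example, the first look at rate 0.15 gives 0.85^12 + 12(0.15)(0.85^11) + 66(0.15²)(0.85^10) = 0.142 + 0.301 + 0.292 = 0.736, against 0.74 in the plan. By 24 subjects:

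| True rate | Protocol Table 29 / SAP Table 4 | Exact | Average N, plan | Average N, exact |
|---|---|---|---|---|
| 0.05 | 1.00 | 0.9995 | 12.1 | 12.1 |
| 0.15 | 0.92 | 0.920 | 16.2 | 16.3 |
| 0.25 | 0.60 | 0.592 | 28.7 | 28.9 |
| 0.35 | 0.24 | 0.242 | 41.4 | 41.4 |
| 0.45 | 0.06 | 0.064 | 47.7 | 47.7 |

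The plan's figures reproduce to within 0.01 in probability and 0.2 in average N.

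**Step 2: apparent rate.** Subjects already negative count as conversions; the rest convert at rate p. So apparent rate = q + (1 − q)p, and the upward bias is q(1 − p). At p = 0.15:

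- q = 5%: 0.05 + 0.95 × 0.15 = 0.1925
- q = 10%: 0.10 + 0.90 × 0.15 = 0.235 (bias 8.5 points)
- q = 20%: 0.20 + 0.80 × 0.15 = 0.32 (bias 17 points)

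For an inactive drug (p = 0) the apparent rate is q itself.

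**Step 3: effect on the futility rule.**

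| p | q | Apparent rate | P(stop by 12) | P(stop by 18) | P(stop by 24) | Average N |
|---|---|---|---|---|---|---|
| 0.15 | 0 | 0.150 | 0.736 | 0.895 | 0.920 | 16.3 |
| 0.15 | 5% | 0.1925 | 0.585 | 0.773 | 0.806 | 20.9 |
| 0.15 | 10% | 0.235 | 0.438 | 0.620 | 0.651 | 26.7 |
| 0.15 | 20% | 0.320 | 0.208 | 0.316 | 0.332 | 38.2 |
| 0 | 10% | 0.100 | 0.889 | 0.976 | 0.985 | 13.2 |
| 0 | 20% | 0.200 | 0.558 | 0.748 | 0.781 | 21.9 |

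**Step 4: q that lifts the apparent rate to 25%.** q = (0.25 − p)/(1 − p). For p = 0.15 this is 0.10/0.85 = 11.8%; for p = 0 it is 25%.

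**The case against.** Several counter-arguments carry weight.

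- **Permission is by silence.** No passage says that therapy may fall between the qualifying sample and day 1. Criterion 109 describes prior regimens as those used to reach remission before screening, which can be read as preceding the MRD finding. This stands as a limit: nothing shows that interim therapy is expected or common. It does not close the gap, because consolidation and maintenance are named and no order is required.
- **Re-screening is covered.** The Section 7.2.1 condition is not confined to R/R subjects, so as written it also reaches a re-screened MRD+ subject. The gap is first screening with a historical result.
- **The SAP already limits the denominator.** Read literally, a subject not MRD-positive at enrollment is excluded. But with no repeat marrow required, status at enrollment is presumed from the older sample. Text directly after the definition, before the 25% statement and in Section 7.5.2 is redacted and may qualify the endpoint.
- **q may be small.** It is the share treated in the interim times the share cleared. If interim therapy cleared 25% (assumed), q = 10% needs 40% of subjects treated and q = 20% needs 80%. At 50% clearance (assumed), the shares are 20% and 40%.
- **Limited stakes.** Conversion is a secondary endpoint of a phase 1 safety study, reported descriptively with 80% intervals.

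A reader might infer that the futility rule is defeated. The documents do not support that: they give no q, and an inactive drug is still stopped with probability 0.985 at q = 10%.

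**Conclusion.** The gap is present in the readable eligibility and sampling text. On first screening, a marrow result up to 3 months old establishes MRD positivity, and no visible rule requires it to follow the last anti-leukemic therapy. Conversion may therefore be overstated, by q(1 − p), and the futility rule weakened.

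How much is unknown. For a drug with true conversion 15%, the loss is noticeable at q = 5% (0.92 to 0.81) and serious at q = 20% (0.33). For an inactive drug the rule holds well at q = 10% and falls to 0.78 at q = 20%. These figures assume that already-negative subjects remain negative and are counted, and that the redacted text does not deal with the matter. This is worth correcting before MRD+ expansion enrols, since day-1 marrow status cannot be recovered afterwards. It does not show that conversions will be spurious.

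**What to change.** 1. **Eligibility.** In criterion 109 and Section 7.5.2.1, carry over the Section 7.2.1 condition: a historical MRD result counts only if no anti-leukemic therapy was given between that sample and day 1. The waivers in Sections 7.2 and 7.5.2 and in Table 25 should refer to it so that they do not say otherwise. Cost: a few candidates would need a newer marrow result or would not qualify.

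2. **Analysis.** In SAP Section 9.5.2, add a sensitivity analysis of MRD conversion excluding subjects who had anti-leukemic therapy between the qualifying sample and day 1. Prior cancer therapies are already collected (Protocol Section 7.3.3), and SAP Appendix G already handles their dates. The date of the qualifying sample must also be in the database; the documents do not say whether it is. The exclusion rests on a pre-treatment fact, so it does not select on outcome. Cost: one extra table and no new procedure.

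3. **Futility.** Keep the boundaries on the first 12, 18 and 24 treated subjects, and show the sensitivity result beside them as context for the decision. Recounting after exclusions would change the denominators, and Table 29 would no longer describe the rule.

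4. **Blood MRD.** Use the pre-dose day-1 whole-blood result (Tables 22 and 23) as supportive information only. Eligibility rests on marrow, and nothing in the documents shows that blood can replace it as baseline.
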